After letters from the provider practices of the 3 participating clinical sites have been mailed to eligible patients or they have been notified of the study by their provider, CHWs will contact patients via mailing and phone calls to invite them to enroll into the intervention. CHWs will call patients a maximum of ten times over a two-week period at varying times of day to invite them to enroll into the study. In addition, list of eligible treatment participants will be shared with primary care physicians who will be encouraged to refer patients to contact CHWs during routine visits. CHWs will also table at primary care provider (PCP) clinics and community events to enhance recruitment and enrollment. During the recruitment call, CHWs will conduct a brief screening to confirm eligibility (see Screening Form). If eligible, patients will be invited to complete an in-person consent form (See Consent Brochure and Consent Signature Page for CHW Intervention) and survey (see Participant Survey) that assesses baseline demographic and logistical information, such as preferred language and session availability. Participants must sign a consent form in order to participate, which will be administered by the CHW or bilingual study coordinator.

Surveys will be collected from all participants at baseline and 6 months. Baseline surveys will be conducted by a CHW or bilingual study coordinator immediately following consent. Six-month surveys will be conducted in person by a study staff within two weeks of completion of the CHW coaching component of the intervention. Survey measures will be developed based on their 1) brevity; 2) presence of domains with face validity for Asian American or low literacy communities; and 3) valid psychometric properties, thus enhancing scientific rigor. Survey measures include weight and blood pressure measurements, as well as questions about self-efficacy, medication adherence, and referrals to social services.

Patient-engagement measures: Contact with eligible treatment group participants will be collected in REDCap or on paper-based CRFs, including phone contact attempts, patients' intervention status (declined, enrolled, not reached etc.), completion of intervention activities (such as health education sessions and phone-based health coaching), and completion of data collection, referrals, and intervention activities across sites and CHWs.

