Clinic to sign the consent form and complete the baseline survey. Control participants will not be contacted during the intervention and will only be contacted once the intervention with treatment participants has been completed; those who were control in the first wave of recruitment can then be enrolled in the second wave. Due to the study funding period, those in the second wave control arm will be offered education sessions as a point of service and not as part of research.

CHW Intervention Period

There is a 6-month intervention period immediately following recruitment. Each session will be held multiple times throughout the month to accommodate a variety of schedules by the treatment participants. Month 1 has participants coming to Session 1 followed by one follow-up phone call. Month 2 has participants coming to Session 2 followed by one follow-up phone call and then one in person visit at the participant's home or at local meeting point used for a session. Month 3 has participants coming to Session 3 followed by two follow-up phone calls within the month. Month 4 has participants coming to Session 4 followed by one follow-up phone call and then one in person visit at the participant's home or at local meeting point used for a session. Month 5 has participants coming to Session 5 followed by two follow-up phone calls within the month. Month 6 concludes the intervention period with an endpoint survey and completion certificate.

Provider Surveys

Over the course of 2 months, providers at participating practices will be invited to complete the Provider Survey via email link. Paper surveys will also be available for those who prefer to fill out the survey in hard copy. No undue pressure will be given to subjects for participation as the participation is entirely voluntary and will be described via email or verbally to the invited participants (See Invitation Script and Elements of Informed Consent for Provider Survey).

Key Informant Interviews

Over the course of 2 months, participating providers and community health workers will receive an invitation to participate in the interview (See Invitation Script and Elements of Informed Consent for Key Informant Interview). No undue pressure will be given to subjects for participation as the participation is entirely voluntary (See Verbal Consent Script for Key Informant Interview).

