The interviews will be completed in-person or virtually via Zoom (Emory University has HIPAA compliant Zoom accounts which have been institutionally approved for telemedicine, see supporting documentation) to accommodate the current COVID-19 situation. The method (face-to-face vs. virtual) will be determined at the discretion and preference of the participants, while following institutional regulations for COVID-19. Recordings will only include audio (not video).

NYULH employees recruited as research subjects are more vulnerable to undue influence or coercion because of the possibility that they may perceive employment or other benefits as dependent upon their participation in research. In addition, NYULH employees may experience increased risk of invasion of privacy or loss of confidentiality.

To minimize these risks, a study team member with no direct supervisory or evaluation responsibilities will be involved in enrolling the CHWs who are NYULH employees who wish to participate in the key informant interview as well as conducting the interview. At time of enrollment, the study team member will emphasize that participation is voluntary and refusal to participate will not affect employment or job performance evaluation. Supervisors of these staff will not be involved in any capacity and will not have access to review any identified transcripts or recordings. All identifying information for employees will be kept strictly confidential following the data security provisions outlined in this protocol.

Focus Groups

A random sample (n=50) of less engaged and more engaged previously enrolled treatment group participants of the CHW intervention will receive an invitation to participate in the focus group (See Invitation Script and Elements of Informed Consent for Focus Group). No undue pressure will be given to subjects for participation as the participation is entirely voluntary (See Verbal Consent Script for Focus Group).

The focus group will be completed in-person or virtually via Zoom (Emory University has HIPAA compliant Zoom accounts which have been institutionally approved for telemedicine, see supporting documentation) to accommodate the current COVID-19 situation. The method (face-to-face vs. virtual) will be determined at the discretion and preference of the participants, while following institutional regulations for COVID-19. Recordings will only include audio (not video).

Characterizing South Asian population

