To determine that the subject or his/her authorized representative understood the information presented, they will be given opportunity to ask questions before giving consent to participate. They can also choose at that time not to be in the study. The individuals authorized to obtain consent will do so by presenting to the subjects the consent form and will verbally read along with the subject and explain the study. The individuals will explain the purpose of the study, the procedures, possible risks and anticipated benefits, that it is voluntary, and how to withdraw if they choose to at a later time. Limited English speaking individuals will be given a translated consent form, and Bengali/Urdu/Punjabi-speaking personnel will obtain consent from them.

D. Debriefing Procedures.

Information will not be withheld from the subjects related to their participation in the study.

E. Consent Forms. Eligible treatment patients will be consented and enrolled to participate in the study (see Consent Brochure/Signature Page for CHW Intervention).

F. Documentation of Consent

Informed consent will be documented by the use of a written consent brochure/signature page to be signed and dated by the subject or the subject's legally authorized representative at the time of consent (See Consent Brochure and Consent Signature Page for CHW Intervention) for all those participants enrolled in the CHW intervention. Individuals authorized to obtain consent will read the consent form to the subject or the subject's legally authorized representative, and the subject or representative will be given adequate opportunity to read it and clarify questions before it is signed. The subject will receive a copy of his/her signed consent form. A translated written consent form will be used for non-English speaking subjects, depending on their preferred language. The informed consent will outline elements of the EHR data collection, CHW group education, one-on-one counseling and survey data collection.

Baseline surveys will also be conducted by Emory study staff with participants within two weeks after consent. The same survey will be completed with intervention participants approximately six months after the start of intervention to evaluate the effectiveness of the CHW intervention, the CHW Intervention 6-month survey will be completed at the last education session.

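### The timing rules for the six-month blood pressure survey conflict, and two of them can be read as depending on attendance in the treated arm only

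*Combined protocol and SAP*

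**What the plan says.** The general intention is clear. Section III.B2, item 1, states: "Surveys will be collected from all participants at baseline and 6 months". The same item makes the survey the carrier of the outcome: "Survey measures include weight and blood pressure measurements".

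The operational timing is given in several ways:

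- Section III.B2, item 1: "Six-month surveys will be conducted in person by a study staff within two weeks of completion of the CHW coaching component of the intervention".
- Consent section, F. Documentation of Consent, first clause: "The same survey will be completed with intervention participants approximately six months after the start of intervention".
- The same sentence, second clause: "the CHW Intervention 6-month survey will be completed at the last education session".
- Section VI.A, CHW Intervention Period: "Month 6 concludes the intervention period with an endpoint survey and completion certificate". The last session falls earlier: "Month 5 has participants coming to Session 5 followed by two follow-up phone calls within the month".
- Section VII.B1 dates the primary outcome six months from the index office visit.

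For controls, section VII.A says that all take part in the baseline and endpoint surveys, and that they are contacted again once the intervention is complete among treated participants. No individual attendance condition applies to them.

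The plan expects uneven engagement. The focus groups draw on "A random sample (n=50) of less engaged and more engaged previously enrolled treatment group participants". Section III.B2 tracks completion of intervention activities, and sessions carry incentives to keep people attending.

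The model in section VII.B1 defines treatment by randomised arm. Sections VII.B2 and VII.B3 assume 10% loss, that is, 90% followed up in both arms. The plan names no analysis set and gives no rule for missing outcomes.

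**The concern.** Two of the timing rules, completion of coaching and the last education session, are events that a treated participant who drops out of coaching may never reach. If staff follow those rules literally, whether the primary BP is obtained depends on adherence in the treated arm and on nothing comparable in the control arm.

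A model that codes arms as randomised does not cure this. It defines the contrast, but an ordinary logistic regression uses only people with an outcome. If the unmeasured treated participants would have had poorer BP control, the treated proportion is overstated. A larger sample does not remove such a bias; it makes a false positive more likely. Counting unmeasured people as uncontrolled is not a safe repair either, because its bias depends on how missingness differs between arms.

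**Working it through.** **1. The plan's own sample size (section VII.B2).** Inputs: 15% versus 35%, two-sided 0.05, 80% power, 10% loss. With pooled variance, n per arm = [1.96·√(2·0.25·0.75) + 0.8416·√(0.35·0.65 + 0.15·0.85)]² / 0.20² = 72.4, so 73. Allowing for loss, 73/0.9 gives 82 per arm (164 in total) and 73 × 1.1 gives 81 (162). The stated 162 is reproduced, and power at 81 × 0.9 = 72.9 per arm is 80.3%. The sample-size figure is not at fault.

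**2. Which anchors need attendance?**

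| Rule | Needs the person to attend or finish? |
|---|---|
| All participants at 6 months (III.B2) | No |
| Two weeks from completing coaching (III.B2) | Yes, if completion is read per person |
| About six months from start (consent section, F) | No |
| Last education session (consent section, F), in Month 5 by VI.A | Yes |
| Month 6 (VI.A) | No |
| Six months from index office visit (VII.B1) | No |
| Controls: when the intervention is complete in the treated arm (VII.A) | No |

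One sentence in the consent section holds both a calendar anchor and an attendance anchor. By the schedule they fall in different months.

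**3. What selective measurement would do.** The documents give no stopping rate and no outcome rate for stoppers, so these are assumptions: no true effect; 15% control in each full arm; a share s of treated participants stop and are unmeasured; their control rate is r; 90% of controls are measured at random.

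- Rate among measured treated participants: p = (0.15 − s·r)/(1 − s).
- False difference: d = p − 0.15.
- Measured numbers: n₁ = N(1 − s) and n₀ = 0.9N, for N randomised per arm.
- Rejection rate: Φ((d − 1.96·SE₀)/SE₁) + Φ((−d − 1.96·SE₀)/SE₁), with SE₀ pooled and SE₁ unpooled.

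Example: s = 0.30, r = 0.05, N = 326. Then p = (0.15 − 0.015)/0.70 = 0.1929 and d = 4.3 points. With n₁ = 228.2 and n₀ = 293.4, SE₀ = 0.0331, SE₁ = 0.0334 and the rejection rate is 25.6%.

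| s | r | d (points) | Rejection, N = 81 | Rejection, N = 326 |
|---|---|---|---|---|
| 10% | 15% | 0 | 5.0% | 5.0% |
| 10% | 10% | 0.6 | 5.1% | 5.4% |
| 10% | 5% | 1.1 | 5.4% | 6.6% |
| 20% | 15% | 0 | 5.0% | 5.0% |
| 20% | 10% | 1.3 | 5.5% | 6.9% |
| 20% | 5% | 2.5 | 6.9% | 12.6% |
| 30% | 15% | 0 | 5.0% | 5.0% |
| 30% | 10% | 2.1 | 6.4% | 10.3% |
| 30% | 5% | 4.3 | 10.2% | 25.6% |

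**4. If control losses are selective too.** Suppose the 10% of controls lost also have rate r. The measured control rate becomes (0.15 − 0.1·r)/0.9, which is 15.6% for r = 10% and 16.1% for r = 5%. With 10% unmeasured in the treated arm, the difference is 0. With 20% it is 16.3 − 15.6 = 0.7 or 17.5 − 16.1 = 1.4 points. With 30% it is 17.1 − 15.6 = 1.6 (before rounding) or 19.3 − 16.1 = 3.2 points.

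**The case against.** A reader might infer that treated participants who stop coaching have no scheduled primary reading at all, and that the trial therefore compares coaching completers with all controls. The documents do not support that. Section III.B2 says that all participants are surveyed at 6 months. The consent section also gives a calendar anchor, about six months from the start. Section VI.A puts the survey in Month 6, which arrives for everyone; listing it beside a completion certificate does not make it conditional on the certificate. Treatment is modelled as randomised.

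Completion of the coaching component can also be read as the end of the programme's coaching phase. Section VII.A uses completion in that sense when it says when controls are contacted, and the rule in III.B2 follows a sentence that covers controls, who have no coaching to complete. The protocol tracks completion of activities separately from completion of data collection. Sampling less engaged people for focus groups is not evidence that they go unmeasured. Finally, the plan expects 90% follow-up in both arms, and at that level the bias is small, or nil if losses are alike.

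Most of this stands. It rules out calling the comparison one of completers by design, and it limits the likely size. It does not remove the last-session rule, the conflict between Month 5 and Month 6, or the absence of any statement that people who stop coaching are still measured. EHR data do not clearly fill the gap: follow-up outcome data are mentioned for one clinic and never tied to the primary BP.

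**Conclusion.** The concern holds in a limited form. The plan intends to measure everyone, but its operational timing rules disagree, and two of them can make measurement depend on attendance in the treated arm only. Selective loss of the primary outcome is a risk of carrying out those rules, not the stated plan.

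The size cannot be derived from the documents. Under the assumed 10% to 30% stopping and 5% to 15% control among stoppers, the false difference is 0 to 4.3 points. The two-sided error rate is then 5.0% to 10.2% at 81 per arm and 5.0% to 25.6% at 326 per arm. The upper ends need 30% unmeasured, much poorer control among them, and control losses that are random. At 10% unmeasured, in line with the plan's own follow-up figure, it is at most 1.1 points and 6.6%. If stoppers resemble the rest, there is no bias.

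**What to change.** In section III.B2 and in item F of the consent section, replace the coaching-completion and last-session anchors with one rule for both arms. Suggested wording: The six-month BP and weight are taken in every randomised participant at a fixed time from randomisation, within a stated window, whether or not they attended sessions or completed coaching. Stopping coaching is not withdrawal from follow-up. Align the Month 6 text in section VI.A with this rule, and use the same starting point for the outcome in section VII.B1.

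The cost is protocol wording and some extra calls to disengaged participants, whom section III.B2 already says will be surveyed.

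Measuring stoppers may reduce the observed difference. If completers reach the planned 35% and stoppers 15%, the treated rate with 10%, 20% or 30% stopping is 0.9·35 + 0.1·15 = 33%, 0.8·35 + 0.2·15 = 31%, or 0.7·35 + 0.3·15 = 29%. The differences are 18, 16 and 14 points. Power stays at 98% or more with about 293 analysed per arm (326 less 10%), but is 73%, 63% and 53% with 73 per arm. That is the effect in those randomised, which the model sets out to estimate.

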A randomized control design will be used to test the efficacy of the CHW intervention to improve HTN control among South Asian individuals with diabetes in Atlanta. The intervention will recruit participants from three clinical sites in Atlanta, GA: 1) The Emory Family Medicine Clinic is located in North Atlanta and serves approximately 1,200 unique South Asian patients annually; 2) Grady Clinic at Brookhaven is a safety net county clinic that sees a high volume of low-income South Asians (approximately 6,000 per year; 3). The Shifa Free Clinic is a community-based free clinic coordinated by the Islamic Circle of North America, Atlanta branch, to serve uninsured and under-insured South Asians in Georgia.. On average, they see 200 unique South Asian patients per month at each site. Both Emory Family Medicine Clinic and Grady Clinic utilize EHR systems which will be used to generate lists of eligible patients for the intervention. Shifa Clinic is currently transitioning to an EHR system, thus patient data will be electronically accessible for patient recruitment and follow-up outcome data. Each of the sites has expressed interest and commitment to participating in the study. The community centers will not be engaged in research, all consenting and procedures will be completed by Emory study staff.

We also anticipate enrolling participants from community-based recruitment with the CHWs referring participants that they meet at South Asian community events and advertising the study. The proposed research design is a modified stepped wedge design, whereby 2 groups will implement the intervention in phases. The time prior to the intervention will serve as the comparison group. Enrolled patients will be randomized to treatment (Group A) and wait-list control (Group B) groups within each site.

There are five primary research groups for this study: 1) 326 treatment participants who will receive the CHW intervention; 2) 326 control participants who may receive the CHW intervention as a point of service at a later point; 3) 10 subjects who will participate in provider surveys; 4) 25 subjects who will participate in qualitative key informant interviews; 5) a retrospective EHR review of characteristics of South Asians seen at Emory Healthcare and NYU hospital system between 2014 and 2019; and 6) 50 subjects who will participate in focus groups.

B2. CHW Component:

1. Data collection and consenting with treatment participants

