
Session 3: Physical Activity
 
 • Caloric intake and energy balance • Benefits and types of exercise • Injury prevention • Incorporating routines • Overcoming barriers • Practice activity and goal-setting 	
 · Discussion of physical activity as essential to physical and mental fitness (eg. encouragement to practice similar discipline in physical activity as in prayer) · Home-based exercise/activities · Practice Activity · Incorporation of culturally appropriate images and language

Session 4: Hypertension and Diabetes Management
 
 • Chronic disease complications • Heart disease and stroke • Communicating with the doctor • Preparing for a doctor's visit • Heart disease and stroke • Staying motivated and goal-setting • Discussion of diabetes complications, heart disease, stroke • Discussion of prevention and interconnectedness of chronic disease • Discussion of cholesterol and fats in diet, blood pressure and salt in diet 	Incorporation of culturally appropriate images

Session 5: Stress and family support
 
 • Effects of stress on health • Stress and anger management • Strategies to manage depression 
Family support and goal-setting
	
 · Discussion of meditation practice · Progressive muscle relaxation for stress relief · Strategies to manage depression; discussion around stigma associated with mental health (eg. depression) · Incorporation of culturally appropriate images and language

A2. Characterizing the Prevalence of Type 2 Diabetes and Prediabetes

Understanding differences/disparities across South Asian populations may help disentangle issues related to genetics, health services, and/or immigration. Given the rapid growth of South Asians in New York and Atlanta and their high burden of diabetes and HTN, a critical need exists to tailor, translate, and disseminate evidence-based interventions to maximize impact in ameliorating co-morbid CVD disparities. Tables 2 and 3 below describe the data to be collected from the electronic health records.

Study Design. Cross-sectional analyses will be conducted using samples of Asian Indians aged 18+ years living in the greater Atlanta area and the New York City area from two large healthcare systems.

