Study Sites. Emory Healthcare is based in Atlanta, Georgia and serves over 611,000 unique patients annually; we conservatively estimate that 1% will be of South Asian origin.

Measures. Variables that will be extracted from the EHR include: 1) study population characteristics (i.e. age, gender); 2) prevalence of diabetes, prediabetes, and hypertension; 3) diabetes risk factors (i.e. smoking, BMI), comorbidities (i.e. lipids), 4) diabetes complications (i.e.. neuropathy, nephropathy, and retinopathy); and 5) diabetes/CVD medications among South Asians.

Data Sources and Collection.

Analysts at each site will associate a specific study number with a specific medical record number in the EHR system. Each study site will maintain the table of study identifiers in RedCap and corresponding

medical record numbers for the duration of the study. After the data extraction, study staff will match the data extract file to the table by medical record number. The medical record number will then be stripped from the extract file and be sent by secure server to NYU. All other potentially identifying data (e.g., zip code, day and month of birth, date of visit) will also be stripped from the dataset prior to storage on the NYU server. The table necessary to link patient identifiers and the study ID will remain at practice sites to ensure that patient confidentiality is maintained.

Analysis. We will conduct cross-sectional analyses, using EHR-based samples South Asians aged 18+ years living in the greater Atlanta and New York City areas from two large healthcare systems.

Prevalence values and 95% CIs will be estimated by study site, sex, age-group, and BMI category. Participant characteristics will be stratified by sex and compared by study using χ^2 test or ANOVA as appropriate. The non-normally distributed variables of fasting and 2-h plasma glucose will be log transformed. The effect of location of residence (Atlanta or New York) on the risk of diabetes and prediabetes will be assessed using standardized polytomous regression. Initially, an unadjusted regression model will be created to compare the individual association between study location and prevalence of diabetes and prediabetes. Subsequent multivariable models were then created to adjust for covariates including age, sex, blood pressure, BMI, and educational status. All analyses will be performed using SAS, version 9.4 (SAS Institute, Cary, NC).

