Exclusion criteria include the following: clinicians who are unable to complete the survey in the English language.

Key Informant Interviews

Inclusion criteria for the interviews are as follows: Adult (18 years and over); must be a provider, clinic manager, or community health worker.

Exclusion criteria include the following: participants who are unable to participate in the interview conducted in the English language.

Focus Groups

Inclusion criteria: Participant previously enrolled in and participated in the CHW intervention (meeting all criteria listed for CHW intervention participant above).

Exclusion criteria: Unwilling to consent to participate

Characterizing Prevalence

Inclusion criteria: a) of South Asian ethnicity (identified by a combination of using natural language processing to identify common South Asian surnames in the EHR, race/ethnicity, and language preference); b) 18 years of age or older; and c) had appointment with a physician for routine non-emergent primary care in the last twelve months.

Exclusion criteria: a) pregnant at time of visit; or b) type 1 diabetes or diabetes secondary to other conditions (e.g. steroid-induced, pancreatic insufficiency, or chemotherapy-induced).

VI. STUDY SCHEDULE

A. Method of Subject Identification and Recruitment

CHW Screening Period

There will be a 1-month recruitment period. All participants will be sent an invitation letter (See Recruitment Letter for CHW Intervention) to participate in the CHW intervention. Invitation letters will be followed up with phone calls by CHWs (See Script for Telephone Screening for CHW Intervention), during which CHWs will explain the study and elements of informed consent. Participant names, telephone numbers, and email addresses will be needed in order for CHWs to contact participants regarding participation in the intervention (See Application for Waiver of HIPAA). In addition, a screening form (See Telephone Screening Form for CHW Intervention) will be completed to verify eligibility. CHWs will call patients a maximum of 10 times over a two-week period at varying times of day to invite them to enroll into the study. Once the participants agree to enroll in the study, they will come into the Emory Dunwoody

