We will conduct cross-sectional analyses, using EHR-based samples South Asians aged 18+ years living in the greater Atlanta and New York City areas from two large healthcare systems. Prevalence values and 95% CIs will be estimated by study site, sex, age-group, and BMI category. Participant characteristics will be stratified by sex and compared by study using χ^2 test or ANOVA as appropriate. The non-normally distributed variables of fasting and 2-h plasma glucose will be log transformed. The effect of location of residence (Atlanta or New York) on the risk of diabetes and prediabetes will be assessed using standardized polytomous regression. Initially, an unadjusted regression model will be created to compare the individual association between study location and prevalence of diabetes and prediabetes. Subsequent multivariable models were then created to adjust for covariates including age, sex, blood pressure, BMI, and educational status. All analyses will be performed using SAS, version 9.4 (SAS Institute, Cary, NC).

B2. Power Calculation.

We conservatively estimate a 20% difference in effect size (i.e., BP control) when comparing intervention and control group participants. Our power calculation was based on our previous studies. Based on results from these studies, at six-month follow-up we conservatively assume a 15% BP control rate for the control group and 35% BP control rate for the treatment group. In our previous work, BP control rates at baseline varied; however, in the proposed study all participants will have uncontrolled BP at baseline. Further, in our past work control group participants experienced almost no change in BP control at follow-up; here we conservatively estimate a 15% BP control rate at follow-up. Accrual of 162 participants, evenly randomized to intervention or control groups, will provide greater than 80% power to detect this difference, using a 2-sided, 0.05-level test (i.e., approximately 81 intervention and 81 control participants). These calculations assume a 10% loss to follow-up.

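### The EHR analysis promises an effect of living in Atlanta or New York, but with one health system per city it can only compare Emory patients with NYU patients

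*Combined protocol and SAP*

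**What the plan says.** The target is named in section IV.A2 (Analysis): "The effect of location of residence (Atlanta or New York) on the risk of diabetes and prediabetes will be assessed using standardized polytomous regression". Section VII.B1, under the Specific Aim 3 analysis, repeats it: "The effect of location of residence (Atlanta or New York) on the risk of diabetes and prediabetes will be assessed". In both places the next sentence gives the exposure a different name: "an unadjusted regression model will be created to compare the individual association between study location and prevalence of diabetes and prediabetes". The later models adjust for age, sex, blood pressure, BMI and education.

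The samples are people "living in the greater Atlanta and New York City areas from two large healthcare systems". Section III.B1 names the two systems: "a retrospective EHR review of characteristics of South Asians seen at Emory Healthcare and NYU hospital system between 2014 and 2019".

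Section V.A (Characterizing Prevalence) has three inclusion criteria: South Asian ethnicity, age 18 or over, and that the patient "had appointment with a physician for routine non-emergent primary care in the last twelve months".

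On data transfer, IV.A2 says: "All other potentially identifying data (e.g., zip code, day and month of birth, date of visit) will also be stripped from the dataset". This happens before storage on the NYU server, and VII.B1 gives NYU the lead in the analysis.

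The plan mentions 95% confidence intervals for prevalence values. It describes no interval or variance method for the regression coefficient.

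**The concern.** The exposure is named as where people live. What the analysis file can hold is which health system supplied the record. These are different quantities if the two systems differ in catchment, payer mix, testing or coding.

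Such differences matter here because the diabetes and prediabetes definitions printed in Table 2 (New York column) are built from coded encounters, prescriptions and repeated A1C results. A patient who is not tested, coded or treated cannot become a case, so recorded prevalence depends partly on how a system practises.

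If the plan is followed as written, a difference of that kind would be estimated under the label of a residence effect. The plan states no limitation on this point.

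**Working it through.** No power, effect size or interval is stated for the city comparison, so there is no figure to reproduce. The check is one of identifiability.

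**1. Cities and systems.** Two cities and two systems (III.B1, IV.A2) give 2 / 2 = 1 system per city.

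| | Emory | NYU |
|---|---|---|
| Atlanta | observed | empty |
| New York | empty | observed |

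**2. What the model can estimate.** Let C be the city indicator and S the system indicator. For outcome k (diabetes or prediabetes, each against neither):

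log-odds_k = a_k + b_k·C + g_k·S + covariates

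In every record C = S, so this becomes:

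log-odds_k = a_k + (b_k + g_k)·C + covariates

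Only the sum b_k + g_k is estimable. The pair (b_k + d, g_k − d) gives the same likelihood for every d. The columns for intercept, C and S have rank 2, not 3.

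**3. Whether covariates or numbers help.** Age, sex, blood pressure, BMI and education vary between patients and leave C = S untouched. The only patient count that can be derived is Emory's: 611,000 × 1% = 6,110 South Asian patients a year (IV.A2), before the primary-care criterion is applied. No NYU count is given. The rank is the same at any count.

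**4. Whether residence is made operational.**

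| Place | Residence |
|---|---|
| Sample descriptions (III.C3, IV.A2, VII.B1) | Described in words as living in the two areas |
| Measures list (IV.A2) | Not listed |
| Table 2, row labels | No row |
| Inclusion criteria (V.A) | Not among criteria a to c |
| File stored at NYU (IV.A2) | Zip code removed |

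The description exists, but nothing puts it into effect.

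**5. Whether patients are found in the same way.** Table 2 identifies Atlanta patients by last name or spoken language. For New York it adds race/ethnicity as a further route. Section V.A gives one rule that combines surname, race/ethnicity and language without distinguishing sites, and section VI.A mentions surnames only. If Table 2 governs, the identification rule is a further site difference carried by the same coefficient.

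**6. The interval.** Let SE be the patient-level standard error and τ the SD between systems within a city.

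- Target is the contrast between these two systems' patients: variance = SE².
- Target is a city effect across systems: variance = SE² + 2τ².

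The documents give no τ. One system per city leaves 1 − 1 = 0 degrees of freedom per city to estimate it. At τ = 0 the two variances agree.

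**The case against.** The best defence is that this component is descriptive and modestly framed. Section II presents it as describing variation in risk and as an initial step, and calls the EHR outcomes descriptive. The sentence after the disputed one already speaks of an association with study location. The samples are described four times as residents of the two areas, and removing zip code before storage at NYU does not stop a site from restricting its extract first. One could also say that local health services are part of what location means.

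Much of this stands. It makes this a point about a secondary component, not about the trial's primary outcome. It also means the residence gap is a restriction that was never written down, rather than a complete omission. It does not rescue the promised effect: a local restriction would make the samples match their description but would leave city and system aliased. Nor is one system's practice the same thing as a city's health services.

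Two stronger readings are tempting, and the documents support neither.

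- A reader might infer that the confidence interval is too narrow. No regression interval or variance method is stated. A patient-level interval is right for a contrast between these two systems' patients. It falls short only if a city effect is claimed and τ exceeds zero. Any coverage figure would rest on an assumed τ, and a wider interval would not cure the aliasing.
- A reader might infer that the plan claims this regression can separate health services from genetics and immigration. The sentence in IV.A2 says that understanding differences across South Asian populations "may help disentangle issues related to genetics, health services, and/or immigration". That is hedged background, not a stated property of the model, and it need not be edited.

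**Conclusion.** The residence effect named in IV.A2 and VII.B1 is not identifiable from this design. The coefficient is an adjusted contrast between Emory and NYU South Asian primary-care patients. It mixes any effect of place with differences between the systems and, if Table 2 governs, with different rules for finding patients.

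The aliasing is exact and rests on one fact in the documents: one health system per city. It needs no assumption about prevalence, sample size or variance between systems. How far the contrast departs from a true residence effect, and in which direction, cannot be derived from the documents.

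The blank Atlanta cells in Table 2 are not counted as a fault. The wording and the inclusion rule should be changed because they determine what this analysis may conclude. The randomised comparison is unaffected.

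**What to change.** 1. In IV.A2 (Analysis) and VII.B1 (Specific Aim 3), replace the residence-effect wording with: *the adjusted association between health system (Emory or NYU) and recorded prevalence of diabetes and prediabetes among South Asian primary-care patients*.
2. In the same two places, state that the difference cannot be attributed to residence apart from health-system differences, and that any interval is conditional on these two systems.
3. Define the greater Atlanta and New York City areas. Have each site derive a yes/no in-area flag from home zip code before it is stripped, and add the flag to the section V.A inclusion criteria. This makes the samples match their description; it does not remove the aliasing.
4. Use one South Asian identification rule at both sites for the comparison, and reconcile Table 2, V.A and VI.A with it.

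The cost is text in a few sections and one variable derived locally at each site. The conclusion becomes more modest and the sample may be slightly smaller. Recruitment and trial procedures do not change. If a city effect is truly wanted, several health systems per city would be needed, which is a different study.
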